7.4.3 Vessel diameter, C/V ratio

Calculation of the vessel diameter, and C/V ratio will be achieved via assessment of the three cross-sectional, B-mode scans to be taken with the indwelling tip PIVC in view. The vessel diameter and catheter diameter will be calculated from the horizontal axis using the internal calculations of the clinically approved ultrasound. The data will be reported as the average of the values taken from the three images.

7.4.4 Valve, side branch location

Identification of a valve/s and/or a side branch vessel will be achieved via assessment of the longitudinal, B-mode scans with the indwelling PIVC in view. The number of valves and side branches that are within 1 cm proximal to the PIVC tip will be recorded and reported. Valves and side branches great than 1 cm from the PIVC tip have not been shown to influence blood flow around the catheter and will not be recorded.

7.4.5 Visualization and quantification of intraluminal/intravascular thrombus formation

Visualization and quantification of thrombi will be assessed using three longitudinal, B-mode scans taken where the probe was positioned in-line with the superior surface of the PIVC tip. Intraluminal and/or intravascular thrombus will be recorded as a 'positive' event if the brightness intensity and position of an echogenic mass is maintained throughout three individual scans. The length of the thrombus will subsequently be measured in millimeters. If the thrombus is greater than 5 cm (i.e., 50 mm) in length, the participant will be sent to the medical doctor for assessment of appropriate treatment and the participant's involvement will be terminated (see section 2.3.1). The three-image confirmation approach will be incorporated into the analysis in order to eliminate the potential for false-positives. This is done because wall shadowing, harmonic distortion and operator movement can all contribute to variations (e.g., brightness) in the appearance of the image³⁸.

7.5 Blood analyses

A lipid panel, liver function test, blood glucose test, and complete blood count, including white blood cell differentials, will be acquired from blood samples anticoagulated with EDTA during screening for assessment of inclusion and exclusion criteria. An automated biochemistry analyzer (AU480, Beckman Coulter, USA) will be employed for the lipid panel, liver function test, and blood glucose test. An automated haematology analyzer (Beckman Coulter DxH 500™; Beckman Coulter, USA) will be used for the complete

blood count. The devices will be operated and maintained in accordance with the manufacturer's standard operating procedure. Blood clotting function and platelet aggregation will be assessed from blood samples anticoagulated with Citrate during screening for assessment of inclusion and exclusion criteria. The activated partial thromboplastin time (aPTT), prothrombin time (PT) will be quantified from the average of duplicate measurements, using an automated haemostasis analyser (Diagnostica Stago, STA-R Evolution; Diagnostica Stago, France). The ADP-induced, and Collagen-induced platelet aggregation will be assessed from the average of duplicate measurements, using an impedance aggregometer (Chrono-Log Corporation, USA). The measurements will be performed in accordance with the manufacturer's standard operating procedures.

If blood test results are not normal, a member of the study team will inform the participant. If the Principal Investigator (PI) believes the results may place the participant at increased risk during the study, the participant will not be able to continue in the study. A member of the study team will provide the participant with the relevant test results, if the participant would like to discuss them with his/her healthcare practitioner.

7.6 PIVC-Failure

The definition of PIVC failure in the current study will be defined as: 1) an inability to flush or collect blood through the PIVC or 2) removal of the PIVC based on medical doctor's assessment of an AE. A device rescue decision tree will be utilized to identify if the PIVC has failed.

7.7 PIVC Removal

Upon completion of the protocol or if the PIVC fails, the device and attached dressing will be removed and disposed of according to the Instructions For Use in biohazard bins and incinerated as per Griffith University waste management protocol. Initially, the dressing will be detached from the participant's skin from distal to proximal direction. Once the dressing has been detached the PIVC, needless connector and dressing will be removed (proximal to distal) together from the participant's arm and later assessed for extravenous thrombus (see section 7.8). Upon removal, a cotton ball will be immediately placed over the insertion site to stem bleeding. Once bleeding has stopped, the arm and insertion site will be wiped clean with a ethanol wipe, a fresh cotton ball placed over the insertion site and taped down with 3M Transpore™ tape.

7.8 Extravenous Thrombus Assessment (Post-Removal)

To assess extravenous thrombus in the removed PIVC and needless connector, a camera will be utilized to take digital photographs of the hub of the PIVC (internal surface), the PIVC (external surface), needless connector (internal surface) and material ejected from the catheter tip. For each site (e.g., the hub of the PIVC), the presence or absence of an extravenous thrombus will be recorded.

7.9 Video/Audio or Photography

To assist the sponsor BD in best capturing and evaluating all the study results, a technician may photograph or video procedures conducted throughout the study. The technician will concentrate only on the procedure, but it is possible that the participant's face may be filmed. Participants are given the right to refuse consent for video/photography, per the informed consent document, and may participate in the study if consent for video/photography is refused.

The recording belongs to BD and will be handled with the same confidentiality as all other information obtained from the participant during this research study. Recorded material will be labeled only with the ID

number that was assigned during the study. The participant's identity will not be revealed by any use of the video recording/photography.

7.10 Safety Assessments

7.10.1 Insertion Site Assessment

Participants will be provided instructions to take care of the catheters while they are away from Clinical Trials Unit (see Appendix 16.4). These include, but are not limited to, instructions on how to take care of the device while at home and instructions on how to look out for health-related complications.

Additionally, the document provides instructions on what to do and who to contact if the participant does experience any health-related complications while at home with the indwelling PIVCs. Additionally, a nurse will complete visual inspection of the insertion sites including assessment of redness, swelling or any signs of infection or other complications prior to each blood draw. This assessment will be done according to the Infusion Therapy Standards of Practice guidelines²⁷ using the Visual Infusion Phlebitis Scale.

Where the site assessment indicates a score of ≥ 4 (Table 4), the participant will be referred to the study medical doctor for medical decision. If an adverse event is suspected by the nurse, the patient will be referred to an on-site clinician for assessment and/or clinical decision.

Table 3. Visual infusion phlebitis scale

Score	Observation
0	PIVC insertion site appears healthy
1	One of the following is evident: Slight pain near PIVC insertion site OR slight redness near PIVC insertion site
2	Two of the following are evident: 
 • Pain at PIVC insertion site • Erythema • Swelling
3	All of the following signs are evident: 
 • Pain along path of catheter • Induration (hardening of the tissue) at PIVC site
4	All of the following signs are evident and extensive: 
 • Pain along path of catheter • Erythema (redness) • Induration (hardening) at PIVC site • Palpable venous cord
5	All of the following signs are evident and extensive: 
 • Pain along path of catheter • Erythema (redness) • Induration (hardening) at PIVC site • Palpable venous cord • Pyrexia (fever)

Adapted from 'A battle in vein infusion: phlebitis' ³⁹

7.10.2 Securement Dressing Assessment

A nurse will complete visual inspection of the securement dressing, including the entire infusion system, prior to each blood draw. This assessment will be done according to the Infusion Therapy Standards of Practice guidelines²⁷ and the securement dressing changed if the dressing integrity becomes damp, loosened, visibly soiled, or if moisture or blood are present under the dressing. If the dressing integrity is compromised, a photo will be taken for observational records and as it is not considered an endpoint of the current study, the data will not be assessed.

8 PARTICIPANT DISCONTINUATION/WITHDRAWAL

8.1 Discontinuation/Withdrawal

- A participant may withdraw from the study at any time at his/her own request or may be withdrawn at any time at the discretion of the investigator or sponsor for safety, behavioral, compliance, or administrative reasons. This is expected to be uncommon.
- At the time of discontinuing from the study, any indwelling catheters will be safely removed and disposed of in accordance with the Instructions For Use as per standard protocol without any data collected. Additionally, the sites of insertion will be assessed for signs of infection and extravasation. The participant will be followed-up within 96 hours for participant safety and to ensure no adverse events have occurred following removal of indwelling catheters.
- If the participant withdraws consent for disclosure of future information, the sponsor may retain and continue to use any data collected before such a withdrawal of consent.
- If a participant withdraws from the study, he/she may request destruction of any samples taken and not tested, and the investigator must document this in the site study records.

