8.3 Patient replacement

Any participants lost to the current study (withdrawn or lost to follow-up) will be replaced through normal screening processes and allocated to the incomplete experimental group to ensure at least 20 participant completers for each catheter gauge. Replacement participants will be started in the same order as drop-out/withdrawal; drop-outs will not be considered eligible for readmission due to potential effects of prior catheter placement on subsequent study outcomes.

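### Protocol 8.1 conflicts with 7.6 to 7.8 on a catheter removed for safety: read literally, it loses the post-removal thrombus assessment and lets a failure be handled as a replaceable drop-out

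*Protocol*

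**What the plan says.** **The withdrawal route.** Under Protocol 8.1 a participant may be "withdrawn at any time at the discretion of the investigator or sponsor for safety, behavioral, compliance, or administrative reasons". At discontinuation any indwelling catheters are "removed and disposed of in accordance with the Instructions For Use as per standard protocol without any data collected". Two checks are kept: "Additionally, the sites of insertion will be assessed for signs of infection and extravasation", and "The participant will be followed-up within 96 hours for participant safety". Section 8.3 then provides: "Any participants lost to the current study (withdrawn or lost to follow-up) will be replaced through normal screening processes". The target is at least 20 completers per gauge, and safety withdrawals are not excepted.

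**The failure route.** Protocol 7.6 has two limbs. The first is inability to flush or draw. The second is "removal of the PIVC based on medical" judgement of an adverse event, and SAP 6.6 repeats it. Under 7.7 and 7.8 a failed device is removed, photographed and assessed for extravenous thrombus at the hub, outer catheter surface, connector and ejected material.

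**A case that could go either way.** Under Protocol 7.4.5 a participant with a thrombus longer than 50 mm is sent to the medical doctor, and the participant's "involvement will be terminated (see section 2.3.1"). The cross-reference is to the risk table, not to 7.6 or 8.1.

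**The analysis.** Extravenous thrombus is a listed secondary endpoint (Protocol 3.1, SAP 2.8.2). SAP 2.7 says that it is assessed once the catheter is out, and Protocol 10.6 compares it by chi-squared test at failure or end of protocol. SAP 5.2.1.1 identifies survival events only from the flush and blood-draw variables.

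**The concern.** A catheter taken out because of an adverse event is an outcome in this trial. Section 7.6 makes it a failure, and so part of the primary endpoint. Section 8.1 can make the same event a withdrawal, and 8.3 then brings in a replacement. The two routes differ in what is recorded and in how the catheter may be counted, and the documents do not choose between them.

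Two things are at stake. First, the post-removal device assessment cannot be recovered once the device has been thrown away. Section 8.1 applies to every indwelling catheter, so a problem in one arm also costs the assessment of a working catheter in the other arm, in a design that is paired on length (Protocol 4.2). Second, these withdrawals are not random with respect to the outcome. If they are handled as drop-outs, failure may be understated for the configuration in which they occur.

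**Working it through.** **1. Where each item ends up for a safety removal.**

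| Item | 7.6 to 7.8 (failure) | 8.1 read literally (withdrawal) |
|---|---|---|
| Extravenous thrombus in the removed device | Photographed and recorded | Not collected, either arm |
| Thrombus length on ultrasound | Available | Available: measured before the 50 mm rule can apply (7.4.5) |
| Infection and extravasation check, 96-hour follow-up | Not at issue | Kept (8.1) |
| Adverse event record | Kept | Kept (9.5 covers site problems that lead to withdrawal) |
| Earlier scans and phlebitis scores | Kept | Kept (7.4, 7.10.1) |
| Status of the participant | Failure observed | Withdrawn and replaced (8.3) |

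**2. Whether the analysis rules settle it.** They do not.
- SAP 6.6 counts adverse event removal as failure, but the SAP 5.2.1.1 coding would not pick it up.
- The Evaluable population (Protocol 10.3) requires follow-up to catheter failure or 72 hours. A participant classed as withdrawn with working catheters meets neither condition.
- Protocol 10.4 includes participants who withdraw consent by imputation, while SAP 5.2.5 rules imputation out.
- SAP 5.2.3.1 tabulates adverse event as a reason for removal, which helps the complication tables but not the primary analysis.

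**3. The plan's own figure.** SAP 2.4 gives power 0.8054 for 19 + 20 = 39, medians of 1 and 3 days, 3 days of follow-up, two-sided alpha 0.05 and zero loss. With exponential survival the 3-day failure probabilities are 1 − 0.5^3 = 0.875 and 1 − 0.5^1 = 0.500. Expected events are 19 × 0.875 + 20 × 0.500 = 26.625. The Schoenfeld formula gives Φ(√(26.625 × 19/39 × 20/39) × ln 3 − 1.96) = Φ(0.87) = 0.809, and a Lakatos-type calculation gives 0.806. The planning inputs reproduce.

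**4. How often it might arise (assumed; the documents give no rate).** P(at least one among 40) = 1 − (1 − r)^40.

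| Risk r per participant | Expected among 40 | P(at least one) |
|---|---|---|
| 1% | 0.4 | 0.33 |
| 2.5% | 1 | 0.64 |
| 5% | 2 | 0.87 |
| 10% | 4 | 0.985 |

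**5. Failure proportion in one configuration (assumed).** Take 20 completers' catheters with 10 failures, and k further catheters removed for safety. Left out: 10/20 = 50.0%. Counted: (10 + k)/(20 + k), that is 11/21 = 52.4%, 12/22 = 54.5% and 13/23 = 56.5% for k = 1, 2 and 3. The understatement is about 2 to 7 percentage points.

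**6. Length comparison (simulated power).** SAP 2.4 inputs, 2,000 runs per cell, independent arms, with 20% of failures in the named arm assumed to be safety removals. The Monte Carlo error is about √(0.8 × 0.2/2000) = 0.009.

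| Safety removals fall in | Counted as failures | Replaced and left out | Censored at removal |
|---|---|---|---|
| Short catheters only | 0.80 | 0.74 | 0.56 |
| Long catheters only | 0.81 | 0.87 | 0.90 |
| Both equally | 0.81 | 0.84 | 0.73 |

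The last column shows what could follow if the SAP 5.2.1.1 coding is applied as written. The SAP does not say that such catheters are censored, so this is also an assumption.

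**The case against.** The strongest reply is that the plan already has a route that keeps the data. Section 7.4.5 sends the participant to a doctor; removal on a doctor's assessment of an adverse event is failure under 7.6, and 7.7 and 7.8 then require the device assessment. Section 7.6 works at catheter level and 8.1 at participant level, so they need not contradict each other. Withdrawals are expected to be uncommon, and this is a feasibility study without acceptance criteria.

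Much of this stands. The loss is what 8.1 produces if followed literally; it is not certain to happen. But both sections can apply to the same removal, 8.1 names safety as a ground, and nothing gives 7.6 priority.

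A reader might also infer that the worst complications vanish from the trial and are swapped for completers. The documents do not support that. Thrombus length has been measured before the 50 mm rule acts, adverse events are recorded, and a phlebitis score of 4 or more leads to referral, not to automatic withdrawal. Section 8.3 adds participants; no text deletes the data of those replaced, and safety withdrawal is not among the data exclusions in SAP 6.2.1.

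For the same reason, a calculation that strikes k failures from 20, such as (10 − k)/(20 − k) = 47%, 44% and 41%, presumes a deletion that the plan does not order. A gauge group also holds 40 catheters, not 20, so any such figure must say which unit it uses.

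**Conclusion.** The point holds as an unresolved conflict with a definite consequence on one reading. If 8.1 governs, extravenous thrombus is not assessed for either catheter of a participant withdrawn for safety, and a removal that 7.6 calls a failure may be handled as a replaceable drop-out. The SAP 5.2.1.1 event coding adds to the risk, because even under 7.6 such a removal would not register as a primary event.

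The size is unknown. The 2 to 7 points in failure proportion rest on an assumed 1 to 3 safety removals beside 10 failures in 20 catheters of one configuration, and on those removals being left out, which no passage orders but which the Evaluable definition and the event coding could bring about. A reader might expect the bias always to favour the longer catheter or always to hide its benefit. The simulation shows that it depends on where the removals fall, and the documents do not say where that will be. The point should be settled before analysis, because each participant is 5% (1/20) of a gauge group. The clinical stopping rule is not judged here.

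**What to change.** **Protocol 8.1.** Reconcile it with 7.6 to 7.8. For withdrawals by the investigator or sponsor for safety, where consent to data continues, delete the clause that no data are collected. Record the removal time and reason and the 7.8 device assessment for each catheter.

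**Protocol 8.3.** State that a participant with a failure under the second limb of 7.6 is not a drop-out for replacement, and that any replaced participant stays in the primary and complication analyses.

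**SAP 5.2.1.1.** Add adverse event removal to the event coding, so that it agrees with SAP 6.6. Without this the protocol edits would not reach the primary analysis. Censor the contralateral catheter at its removal time if it is still working. That censoring may itself be informative, since both catheters share one participant, and the report should say so.

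**Cost.** Wording changes in both documents, and a few minutes at removal for assessments already done when a catheter fails or completes. A group may end with slightly fewer than 20 full-dwell completers. The criteria for ending a participant's involvement are not changed.

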8.2 Lost to Follow-Up

A participant will be considered lost to follow-up and summarily withdrawn if he or she fails to return for consecutive study visits post PIVC insertion (Visits 2 through 5).

The following actions must be taken if a participant fails to return for/complete a required study visit:

- The site must attempt to contact the participant and attempt to schedule catheter removal and follow-up as designated by Visits 5 and 6 procedures.
- These contact attempts should be documented in the participant's study record.
- Should the participant continue to be unreachable, he/she will be considered to have withdrawn from the study.
- Participants lost to follow-up after Visit 1 but successfully contacted prior to PIVC placement may be allowed to continue with Visits 2 through 6 at PI discretion.

8.3 Patient replacement

Any participants lost to the current study (withdrawn or lost to follow-up) will be replaced through normal screening processes and allocated to the incomplete experimental group to ensure at least 20 participant completers for each catheter gauge. Replacement participants will be started in the same order as drop-out/withdrawal; drop-outs will not be considered eligible for readmission due to potential effects of prior catheter placement on subsequent study outcomes.

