Intervention(s)/Procedure(s)	After screening and enrollment, participants will be randomized in order of their enrollment to either 20 or 22G of the BD Nexiva™ PIVC and order of placement location (left or right arm first). The participant will have both the 1 inch and 1.75 inch PIVCs inserted on Study Day 1 (Visit 2), one into each arm. After successful insertion into the lower cephalic vein of the selected arm, the site will be regularly accessed (twice daily) for phlebotomy and then flushed. The site will be assessed visually for tissue effects, skin reactivity, and pain, and using ultrasound for vessel anatomy/dimensions, catheter tip location in the vessel, color, and PWD. After catheter removal there will be a final inspection of the insertion site and securement dressing, assessing for tissue effect, skin reactivity, and pain.		
Investigational Sites	This study is a single-center study that will be conducted at Griffith University Gold Coast Campus, Clinical Trials Unit in Queensland, Australia.		
Data Monitoring Committee	Not applicable.		
Regulatory Status	Registered with Australian TGA: ARTG 243114		

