4.2 Scientific Rationale for Study Design

Given that participant variability (e.g., coagulation and platelet function) may impact study endpoints (e.g., device indwell time and haemolysis)²³, the current study utilizes a simultaneous paired experimental design to assess whether differences in device design (i.e., lengths of 1 inch and 1.75 inch) impact PIVC indwell time; unpaired analysis will be employed to investigate the effects of catheter gauge on PIVC indwell time. PIVC length was selected for paired analysis as it is hypothesized that longer PIVC catheters may extend indwell time based upon catheter tip location within the vessel, increased tip distance from insertion site, and reduced probability of accidental dislodgement. Although gauge is a factor that may impact indwell time, participant screening is conducted to only enroll those with catheter-to-vessel (C/V) ratios no greater than 45%; thus it is anticipated that gauge will have an effect less susceptible to participant variability and was selected for the unpaired analysis. As both device length and gauge are expected to influence haemolysis^{17,20} the study design enables evaluation of both design features.

Identification of device design factors that improve PIVC indwell time and decrease incidence of haemolysis during PIVC-based blood collection is of clinical significance due to the associated benefits for the patient (e.g., uninterrupted medical treatment, and decreased discomfort, pain and anxiety)^{28,29,33}, for the health care worker (e.g., reduced chance of needle stick injuries)²⁸, and for the healthcare institution (i.e., reduced cost of care)^{12,29}.

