5.2 Exclusion Criteria

Participants are excluded from the study if any of the following criteria apply:

- a. History of pro coagulative state/condition (e.g. previous deep vein thrombosis)
- b. Current hypertension (e.g., systolic >139 OR diastolic >89 mmHg)
- c. Currently on any anti-coagulant or platelet inhibitor medication. Use of NSAIDs and aspirin will be documented however not exclusionary.

- d. Hemophilia or any current or history of bleeding disorder or tendency
- e. Presence or report of current blood borne disease/infection (e.g. hepatitis, HIV, leukemia, lymphoma)
- f. Difficult vascular access (i.e., vein must be readily palpable and cannulatable – no less than ~2.55 mm diameter to maintain $\leq 45\%$ C/V ratio) as indicated by standard 52 of the INS guidelines²⁷
- g. Allergy or sensitivity to chlorhexidine gluconate, isopropyl alcohol, latex, or skin adhesives
- h. BMI $< 18.5 \text{ kg/m}^2$ or $\geq 35 \text{ kg/m}^2$
- i. Positive results for the urine drug screen at screening or check-in (including opiates, methadone, cocaine, amphetamines)
- j. History or presence of alcoholism (self-reported) or drug abuse within the past 2 years
- k. A current or previous medical, physical, mental/cognitive disorders or anatomical conditions that, in the opinion of the investigator, would place the patient at risk, would make them unable to perform study procedures or has the potential to confound interpretation of the study results. (e.g., musculo-skeletal injury, chronic back pain)
- l. Employed by Becton Dickinson, Teleflex Medical, Smiths Medical or B Braun (conflict of interest)

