6.5.1 Randomization

Participants will be randomized using R statistical software*¹ (R 3.6.2 or higher). The generation of the randomization list will be conducted by a staff member not involved in data acquisition or analysis. Each randomization number will have a corresponding code (e.g., LA_20G_1.75 – indicating a Nexiva 20G 1.75

*¹ R Core Team. R: A Language and Environment for Statistical Computing. R Foundation for Statistical Computing, Vienna, Austria, 2016. URL <https://www.R-project.org/>.

will be first inserted into the left arm). The participant will then have the other length PIVC of the same gauge inserted into the contralateral arm.

Intervention kits will be created for each participant using large ziplock bags with all necessary (plus extra) consumables inside. Each kit will be separated via separate ziplock bags into consumables required for the right arm and left arm. Once the kits have been created, the appropriate randomization number will be recorded on the outside of each. Subsequently, the corresponding code will be placed in an envelope and sealed with the randomization number written on the outside of the envelope. These envelopes will be produced in duplicate with the second envelope sealed in a locked cabinet in the CTU for the circumstance where unblinding is required. Thereafter, the randomization list excluding the corresponding code will be given to the postdoctoral research fellow for storage until a randomization number is requested for the study.

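### Replacement participants go to whichever gauge group is short, so the unpaired gauge comparison loses concealed random allocation for them; the likely effect is small and the repair is cheap.

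*Protocol*

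**What the plan says.** **Main cohort.** The Protocol Synopsis (1.1) states that, after screening and enrolment, "participants will be randomized in order of their enrollment to either 20 or 22G". Protocol 6.5.1 describes the concealment: "the corresponding code will be placed in an envelope and sealed with the randomization number written on the outside of the envelope", and "the randomization list excluding the corresponding code will be given to the postdoctoral research fellow for storage".

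**Replacements.** Of participants who leave the study early, Protocol 8.3 says that they "will be replaced through normal screening processes and allocated to the incomplete experimental group". The stated aim is no fewer than 20 people completing in each gauge group. The section adds: "Replacement participants will be started in the same order as drop-out/withdrawal". SAP 2.3.1 repeats the randomisation text and does not mention replacements.

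**The comparison affected.** Length is paired within participant. For gauge, Protocol 4.2 says "unpaired analysis will be employed to investigate the effects of catheter gauge on PIVC indwell time". Gauge is one of the two indwell-time hypotheses (Protocol 3.2.1; SAP 5.2.1.1).

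**Who knows the gauge.** The trial is open-label (Protocol 4.1). Protocol 6.5.2 blinds most staff but not the inserter or the study manager, who is the research assistant. The device is colour coded by gauge (Protocol 6.1).

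**Room for judgement.** Protocol 5.2 requires that the "vein must be readily palpable and cannulatable", gives an approximate diameter limit of 2.55 mm, and has an item resting on the investigator's opinion. SAP 2.2 lets a medical monitor admit people who do not meet all criteria.

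**The concern.** Concealment keeps the decision to admit a person independent of the group that person will enter. The plan secures this for the main cohort and then, by an explicit rule, gives it up for replacements. Anyone who knows the drop-out's gauge knows which group is short, and so which gauge the next person screened will receive.

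This matters for gauge because that comparison is between participants, with about 20 per group, and has only random allocation to make the groups alike. Vein size is an obvious route for selection, because the room left by the catheter-to-vein limit differs by gauge (see the working). Protocol 13.2 also requires vascular ultrasound training for the research assistant, so a role that knows gauge is trained in the technique used to assess veins. The within-participant length comparison is not broken by how gauge is assigned.

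**Working it through.** **1. The plan's own figure.** The calculation in SAP 2.4, also applied to gauge, uses 19 and 20 participants, medians of 1 and 3 days, 3 days of follow-up, no loss and two-sided alpha 0.05. With exponential survival, failure by day 3 is 1 − 2^(−3/1) = 0.875 and 1 − 2^(−3/3) = 0.500. Expected events are 19 × 0.875 + 20 × 0.500 = 26.6. Power is 0.806 (Lakatos) or 0.809 (Schoenfeld), against the stated 0.8054, so the figure reproduces. It assumes no drop-out and has no bearing on how replacements are allocated.

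**2. Why selection could depend on gauge.** SAP 5.1.5 gives outer diameters of 1.10 mm (20G) and 0.90 mm (22G). The 45% ratio is reached at 1.10/0.45 = 2.44 mm for 20G and 0.90/0.45 = 2.00 mm for 22G. A 2.2 mm vein is below the common 2.55 mm limit, yet gives 0.90/2.2 = 41% with 22G and 1.10/2.2 = 50% with 20G. Someone who knows that the replacement will receive 22G has an argument for a waiver that is not available for 20G.

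**3. Size of a possible bias.** The documents give no number of replacements and no selection effect, so both are assumed. Let r of the 20 participants in one gauge group be replacements whose hazard is h times that of an unselected participant. Averaging log hazards, the gauge HR is multiplied by h^(r/20). If the replacements are in the other group, the factor inverts.

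As a check, 20,000 trials were simulated with no true gauge effect, exponential survival with median 2 days (assumed), follow-up capped at 3 days, 20 per group and h = 0.5.

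| r | Factor, h = 1/2 | Factor, h = 1/3 | Simulated HR, h = 1/2 | Two-sided 5% logrank rejects |
|---|---|---|---|---|
| 0 | 1.00 | 1.00 | 1.00 | 5.2% |
| 1 | 0.97 | 0.95 | 0.97 | 5.1% |
| 2 | 0.93 | 0.90 | 0.94 | 5.4% |
| 4 | 0.87 | 0.80 | 0.88 | 6.4% |
| 6 | 0.81 | 0.72 | 0.82 | 7.7% |

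The simulation error near 5% is √(0.05 × 0.95/20,000) = 0.15 points, so one replacement cannot be told from none.

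**4. Against sampling error.** At 20 + 20, the SAP's medians give 20 × 0.875 + 20 × 0.500 = 27.5 events, so the SE of log HR is about 2/√27.5 = 0.38. For h = 1/2, the shift is (2/20) × ln 2 = 0.069 with two replacements, or 0.18 SE, and 0.139 with four, or 0.36 SE.

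**5. Cost of a gauge analysis without replacements.** On the SAP inputs (Lakatos), power is 0.813 at 20 + 20. With 1, 2, 3 or 4 participants left out of each group it is 0.793, 0.771, 0.748 or 0.722.

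**The case against.** The strongest reply is that the text does not show anyone judging eligibility with the gauge in hand. That is right. A reader might infer that the gauge is known to whoever screens, but no section names that person, and most staff are to be blinded. What the documents support is that the gauge is fixed beforehand and can be worked out by at least two roles, with nothing keeping that knowledge away from eligibility decisions.

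A reader might also take the sentence on starting order to mean that a replacement inherits the drop-out's arm and length sequence. It may only mean that replacements start in the sequence in which drop-outs occurred, so the stronger reading is not established.

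It would also go too far to say that steering could not be seen. SAP 6.3 and Table A.3.1 summarise the baseline catheter-to-vein ratio by gauge. Catheter diameters are fixed, so vein diameter can be recovered and a marked imbalance would show. The ratio also enters the Boruta work (SAP 5.2.2.3). But the covariates named for the primary Cox model are gender, age, BMI and dominant arm (SAP 5.2.1.1). Vein size is not among them, and replacements are not flagged.

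Most other criteria are numeric, the 2.55 mm limit is the same for both gauges, and nothing shows that judgement has followed gauge. Withdrawal is expected to be uncommon (Protocol 8.1), and catheter failure is the endpoint, not a ground for replacement. This is a feasibility study without acceptance criteria (SAP 2.9). All of that stands and limits the size of the problem. It does not restore concealment.

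**Conclusion.** The point holds as a weakness in allocation. By a stated rule, replacements enter the gauge comparison without random, concealed assignment. The documents do not support the inference that the gauge result is invalid or that steering will occur. Bias needs three things: someone who knows the short group influencing admission, that influence being related to catheter survival, and enough replacements to matter.

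If selection halved the hazard of every replacement in one group, one or two would shift the gauge HR by 3% to 7% and leave the test size close to nominal. Four would shift it by about 13% and bring the test size to about 6.4%. With no steering the shift is nil. The number of replacements and the strength of selection are both assumptions. The change is worth making because it costs almost nothing and gauge is half of the primary question.

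**What to change.** 1. Amend Protocol 8.3. Same-gauge replacement may stay, which keeps the aim of at least 20 completers per gauge. The list-holder keeps the replacement's code sealed and withholds it from staff who screen, perform sonography or judge eligibility until eligibility and the Day 1 recheck are signed off. Those staff should also not be told which group is short.
2. State in 8.3 what starting in the same order means: the sequence of starts, or the arm and length sequence as well.
3. Flag replacements in the dataset and report their number by gauge.
4. Add to the SAP a sensitivity analysis of gauge restricted to originally randomised participants. It removes the replacements but does not make good the information lost with the drop-outs.
5. Reconcile 8.3, which bars drop-outs from readmission, with SAP 6.2.1, which asks participants excluded for certain insertion errors to re-enrol after 2 weeks. Say how gauge is then allocated.

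The cost is minor logistics, a few sentences, and slightly lower precision in the sensitivity analysis. Fully random reserve codes are an alternative. At an 18/22 split, power would be 0.800 to 0.820, depending on which group is larger, against 0.813 at 20/20. They would give up the guaranteed 20 completers per gauge, so they are an option and not a requirement.
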